6.5.1 Administration of PRO questionnaires

Paper questionnaires will be given to the patient at baseline, at Day 29 and then every 12 weeks (+/- 7 days) for 156 weeks, then every 24 weeks (+/- 7 days) or until the data cut off for the primary analysis. In addition, Quality of Life questionnaire will be collected at the discontinuation of study treatment visit and 30 days post last dose. Patients who had RECIST 1.1 disease progression will complete the questionnaires during the 12 weekly survival follow-ups either in person or over the phone (see [Table 3](#) and [Table 4](#)). Following collection of the paper questionnaire (in person or over the phone), the site staff can either enter the information directly into the WBDC (RAVE) electronic database system or arrange to have the paper questionnaires transcribed into the WBDC (RAVE) database.

Date 05 November 2021

Each centre must allocate the responsibility for the administration of the questionnaires to a specific individual (e.g., a research nurse, study coordinator) and if possible assign a back-up person to cover if that individual is absent. The AZ Study Delivery Team (or delegate) will provide relevant training in administration of the questionnaires. The significance and relevance of the data need to be explained carefully to participating patients so that they are motivated to comply with data collection.

The instructions for completion of the PRO questionnaires are as follows:

- It must be completed prior to any other study procedures (following informed consent) and before discussion of disease progress to avoid biasing the patient's responses to the questions
- It must be completed in private by the patient, where a visit to the clinic is not planned, i.e. for patients followed up for survival with no scheduled clinic visits, the site staff will administer questionnaires via telephone.
- The patient should be given sufficient time to complete at their own speed
- The patient should not receive help from relatives, friends or clinic staff to answer the questionnaire. However, if the patient is unable to read the questionnaire (e.g., is blind or illiterate) the questionnaire may be read out by trained clinic staff and responses recorded
- On completion of the questionnaire it should be handed back to the person responsible for questionnaires who should check for completeness

Only 1 answer should be recorded for each question

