Patients known to have deleterious or suspected deleterious germline BRCA mutation/s (gBRCAm i.e., blood) prior to randomisation can enter the study based on this result. The result must be made available to AstraZeneca. In addition the patients must consent to provide 2 blood samples. One sample will be used for a confirmatory Myriad gBRCA test post randomisation using the current commercial Myriad BRCAnalysis® (gene sequencing and large rearrangement analysis), which will be paid for by AstraZeneca.

Patients with unknown BRCA status must consent to provide 2 blood samples for germline BRCA testing and follow all local ethical procedures for genetic testing. One sample will be used to test for BRCA mutations using the current commercial Myriad BRCAnalysis® test prior to study entry. The second is required for a bridging study to validate the companion diagnostic test for olaparib. These samples will be required for the study even if the patients are found not to have a BRCA mutation. When the result from the Myriad test indicates the

patient does have a deleterious or suspected deleterious BRCA mutation, the patient can be randomised into the study.

Patients will be randomised within 8 weeks after their last dose of chemotherapy (last dose is the day of the last infusion).

Randomisation will be stratified by:

• Response to first line platinum chemotherapy (in the opinion of the investigator, clinical complete response (CCR) or partial response (PR)).

Following randomisation patients in both treatment arms will attend clinic visits weekly for the first 4 weeks of treatment (Days 8, 15, 22 and 29). Patients will then attend clinic visits every 4 weeks whilst on study. Patients should continue to receive study treatment for up to two years or until objective radiological disease progression as per RECIST as assessed by the investigator and as long as in the investigator's opinion they are benefiting from treatment and they do not meet any other discontinuation criteria (see Section 5.8 of the Clinical Study Protocol (CSP)). Patients who continue to have evidence of disease that remains stable (i.e. no evidence of disease progression) at two years or those who have progressed may continue to receive study treatment if, in the opinion of the investigator, it is in the patient's best interest. However, if at two years the patient has no evidence of disease, study treatment should be discontinued.

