3.3 Patient Reported Outcome (PRO) Variables

3.3.1 FACT-O

Patient reported health-related quality of life (HRQoL) will be assessed using the Functional Assessment of Cancer Therapy – Ovarian (FACT-O) questionnaire (Basen-Enquist K et al 2001). The FACT-O is composed of the following sub-scales: physical, social/family, emotional, and functional well-being as well as the additional concerns scales consisting of specific ovarian cancer symptoms.

The endpoint for HRQoL analysis will be the Trial Outcome Index (TOI), (Cella D et al 1993) an established single targeted index derived from the FACT-O questionnaire and it is considered to target the most relevant symptoms together with function and physical well-being and can be directly related to signs and symptoms and AEs. The TOI is composed of the following scales of the FACT-O: physical and functional well-being and additional concerns (ovarian cancer subscale).

Data relating to the FACT-O will be self-reported through patient questionnaires according to the study plan. Patients will be asked to report their HRQoL over the course of the previous 7 days. All patients will be asked to complete the FACT-O. The FACT-O questionnaire will be administered at baseline, at Day 29, then in line with the RECIST assessments every 12 weeks (+/- 7 days) for 156 weeks, then every 24 weeks (+/- 7 days) up to the data cut off for the primary analysis. In addition, HRQoL questionnaires will be collected at the discontinuation of study treatment visit and 30 days post last dose. Patients who had RECIST 1.1 disease progression will complete the questionnaires during the 12 weekly survival follow-up visits either in person or over the phone.

The Trial Outcome Index (TOI) score will be derived from the sum of the scores of three of the derived subscale scores; physical well-being (7 items), functional well-being (7 items), and ovarian cancer subscale (11 items) of the FACT-O questionnaire version 4. The total FACT-O score will also be calculated which is made up of the sum of the individual subscale scores: physical well being (PWB), social well being (SWB), emotional well being (EWB), functional well being (FWB) and ovarian cancer subscale (Additional Concerns) (11 items).

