Best overall TOI improvement (in absence of starting any subsequent cancer therapy) will be defined as a change from baseline in the TOI of + 10 points or more (Osoba et al 2005) sustained for at least 28 days, the denominator consisting of a subset of the FAS population who have baseline TOI. It will be derived as the best symptom improvement response the patient achieved, based on evaluable HRQoL data collected from randomisation up to the earliest of starting any subsequent cancer therapy or death. Therefore, at the conclusion of the trial, the following criteria, will be used to assign a best overall score response based on the individual visit responses (Table 6).

Table 6 Health-Related Quality of Life: Change rates - overall score

Best overall TOI score response	Criteria
Improved	Two visit responses of "improved" a minimum of 28 days apart without an intervening visit response of "worsened"
No change	Does not qualify for overall score response of "improved". Two visit responses of either "no change" or "improved and "no change" a minimum of 28 days apart without an intervening visit response of "worsened"
Worsened	Does not qualify for overall score response of "improved" A visit response of "worsened" without a subsequent response of "improved" or "no change" within 28 days.
Other	Does not qualify for one of the above.

In the calculation of the proportion of patients that have a response of Improved, No Change or Worsened, the denominator used in the calculation will use the number evaluable patients with a TOI score at baseline.

Summary measures of overall compliance and compliance over time will be derived for the FACT-O questionnaire. These will be based upon:

- Received forms = number of FACT-O forms received back plus the number not received back where the reason was 'Subject too heavily affected by symptoms of disease under investigation'.
- Expected forms = number of patients still under HRQoL follow-up at the specified assessment time excluding patients in countries with no available translation. For patients that have progressed, the latest of progression and safety follow-up will be used to assess whether the patient is still under HRQoL follow-up at the specified assessment time. Date of study discontinuation will be mapped to the nearest visit date to define the number of expected forms.

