4.2.9 Patient reported outcomes (PROs)

The analysis population for HRQoL data will be the subset of the FAS (ITT set).

It should be noted that some centres erroneously collected patient data using the FACT-O at non-protocol visits. These data will not be used in any analyses or summaries, but will be listed in the appendices and flagged accordingly.

The HRQoL benefit of the long PFS delay with olaparib is expected to be observed when placebo patients require chemotherapy earlier as this is when HRQoL may be expected to deteriorate. It is expected that the stability in "HRQoL" over the 24 months following start of randomised treatment will be longer for patients randomised to olaparib than placebo. This will be investigated using the TOI derived from the FACT-O questionnaire.

Change from baseline TOI scores

Change from baseline in TOI score will be regarded as the primary analysis of the FACT-O questionnaire and will be analysed using a mixed model for repeated measures (MMRM) analysis of the change from baseline (defined as prior to first dose) in TOI scores for each visit.

The primary analysis will be to compare the average treatment effect from the point of randomisation for the first 24 months (which will include analysis visits obtained within the first 24 months, i.e. baseline, day 29 (week 4), weeks 12, 24, 36, 48, 60, 72, 84, 96, see Section 3.3.2) unless there is excessive missing data (defined as >75% missing data). If the time to first subsequent chemotherapy when approximately 50% of placebo patients receive chemotherapy does not occur by 24 months post-randomisation then additional time periods will be analysed and will be included on supportive summaries and graphical displays as appropriate.

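### By-visit FACT-O compliance omits scheduled post-progression forms, so it does not describe missingness in the 24-month TOI comparison and may overstate completeness

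*SAP*

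**What the plan says.** **Collection.** SAP 3.3.1 schedules FACT-O at baseline, day 29 and then with the RECIST visits up to the primary data cut-off. It adds that "HRQoL questionnaires will be collected at the discontinuation of study treatment visit and 30 days post last dose". Collection goes on after progression: "Patients who had RECIST 1.1 disease progression will complete the questionnaires during the 12 weekly survival follow-up visits". Protocol 6.5.1 has the same rule, "Patients who had RECIST 1.1 disease progression will complete the questionnaires during the 12 weekly survival follow-ups either in person or over the phone", and Protocol 6.2.2 repeats it.

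**Compliance.** Further on in SAP 3.3.1, expected forms are those from patients still under HRQoL follow-up. For a progressed patient, "the latest of progression and safety follow-up will be used to assess whether the patient is still under HRQoL follow-up". Evaluable forms are a subset of expected forms; received forms carry no such limit. Three rates follow:

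- overall compliance: patients with an evaluable baseline form and at least one evaluable later form, over those expected at baseline;
- by-visit compliance: patients with an evaluable baseline form and a form at the visit, over those still expected at that visit;
- evaluability: evaluable forms over received forms, by visit.

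**Analysis.** SAP 4.2.9 compares average TOI change over the first 24 months from randomisation (visits to week 96, equally weighted), "unless there is excessive missing data (defined as >75% missing data". It also plans by-visit plots of completed, partly completed and missing questionnaires.

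**The concern.** One SAP section schedules forms after progression and then, for compliance, stops expecting them. Past the cut-off, a returned form counts in neither the by-visit numerator nor its denominator, and an unreturned form is not counted as missing.

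That is the period that matters most for this endpoint. SAP 4.2.9 expects the HRQoL benefit to appear when placebo patients need chemotherapy sooner, which in practice is after progression. A reader judging whether the 24-month comparison can be trusted will look at the compliance table, which is silent about those visits. Under the planning assumptions placebo patients progress earlier, so the omitted share is larger on placebo.

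**Working it through.** The documents give no compliance figure to reproduce. The check therefore compares the texts and then sizes the gap from the planning assumptions.

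**1. When expectation ends.** It ends at the later of progression and safety follow-up, about 30 days after last dose. SAP 1.2 allows that "those who have progressed may continue to receive study treatment", so a patient treated beyond progression stays expected until her safety follow-up. A patient who stops at progression leaves about a month later.

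**2. Whether later forms are analysed.** This is inferred, not stated. SAP 4.2.9 excludes no visit after progression, and its model for treatment-by-visit means uses all visits. Its AUC analysis uses all available scheduled visits and scores deaths as zero up to 24 months. By contrast, SAP 3.3.1 explicitly truncates best TOI response at subsequent therapy, so the SAP states truncation where it is intended.

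**3. Planning inputs (SAP 1.3).** Exponential PFS with medians of 13 months on placebo and 13 + 8 = 21 on olaparib; 391 patients randomised 2:1, about 130 and 261. Check: 13/21 = 0.619, agreeing with HR 0.62. Schoenfeld's formula gives (1.960 + 1.282)² / [(ln 0.62)² × 2/9] = 207 events, against 206 stated.

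**4. Share past the cut-off.** With the cut-off 1 month after progression, f = 1 − 2^(−(t − 1)/median). Week 96 is 96 × 7 / 30.4375 = 22.1 months; week 48 is 11.0 months.

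**5. By-visit compliance.** Assumed completion is 90% before the cut-off and p after it, with p from 50% to 90%. The SAP rule reports 90% whatever p is. The full schedule gives 0.9 × (1 − f) + p × f.

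| Visit, arm | f | Patients past cut-off | SAP rule | Full schedule, p = 50% to 90% |
|---|---|---|---|---|
| Week 48, placebo | 41.4% | about 54 | 90% | 73% to 90% |
| Week 48, olaparib | 28.2% | about 74 | 90% | 79% to 90% |
| Week 96, placebo | 67.5% | about 88 | 90% | 63% to 90% |
| Week 96, olaparib | 50.1% | about 131 | 90% | 70% to 90% |

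For example, week-96 placebo at p = 50%: 0.9 × 0.325 + 0.5 × 0.675 = 0.630.

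**6. Overall compliance.** The denominator is fixed at baseline, so the cut-off cannot shrink it. Dropping later forms from the numerator can only lower the rate.

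**7. Evaluability.** If every received form is in fact evaluable, the rate should be 100%. As written it is 0.9(1 − f) / [0.9(1 − f) + p f]. At week 96 that is about 33% (placebo) and 50% (olaparib) with p = 90%, and 46% and 64% with p = 50%.

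**8. A programming risk.** If the by-visit numerator were taken from received rather than evaluable forms, the rate could exceed 100%. At week 96 with p = 90% it would be 0.9/0.325 = 277% on placebo and 0.9/0.499 = 180% on olaparib.

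**The case against.** A reader might infer that expectation stops at progression and that compliance is therefore overstated. The documents do not support that. The cut-off is the later of two dates, and post-cut-off forms leave the by-visit numerator as well as its denominator. The by-visit rate is inflated only if completion falls after progression. The documents give no figure on that, and telephone completion is provided for. The overall rate is not inflated, and evaluability moves the other way. All of this stands.

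A reader might also infer that the rule disables the 75% missing-data proviso. SAP 4.2.9 does not tie that proviso to expected forms. Even an extreme case does not reach it. With the cut-off at progression (69.2% and 51.7% past it at week 96) and no forms afterwards, data exist for 0.9 × 0.308 = 27.7% of placebo and 0.9 × 0.483 = 43.4% of olaparib patients. That is about 72% and 57% missing, both under 75%.

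Missing forms are not wholly hidden: SAP 3.3.1 requires reasons for missing assessments, and SAP 4.2.9 plans plots. This helps only in part, because the plots state no denominator for missing.

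Finally, TOI change is derived wherever data exist, so no estimate uses the compliance rate. Protocol 6.5 says questionnaires stopped after the primary analysis, so only reporting can change. That limits the consequence, but the stated rates still do not match the SAP's own schedule.

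**Conclusion.** The mismatch is real and can be read from the text. By-visit compliance covers only part of the scheduled forms and does not describe missingness in the 24-month TOI comparison. It may overstate completeness, more so on placebo. The evaluability rate divides a restricted numerator by an unrestricted denominator and is too low.

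At week 96 the illustration gives 90% reported against 63% to 90% on placebo and 70% to 90% on olaparib; at the upper end there is no distortion. It rests on completion rates that are assumed (and equal in both arms), on the planning PFS medians, and on a cut-off one month after progression. The omitted shares are upper bounds: PFS events include deaths, and patients treated beyond progression stay expected longer. The effect is on descriptive tables and on how the TOI result is read, not on the result itself.

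**What to change.** In SAP 3.3.1, define expected forms at each visit as all patients alive, not withdrawn from the study, with an available translation and not past the primary data cut-off, whether or not they have progressed. Limit received and evaluable forms to that same set. Report compliance by arm and visit, split before and after progression.

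The cost is SAP wording and re-run descriptive tables on data already held. Reported compliance may come out lower. The TOI estimate does not change.

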3.3.2 EQ-5D-5L (exploratory analysis)

The EQ-5D-5L, developed by the EuroQol Group, is a generic questionnaire that provides a simple descriptive profile and a single index value for health status for economic appraisal. The questionnaire comprises six questions that cover five dimensions of health (mobility, self-care, usual activities, pain/discomfort and anxiety/depression) and how the patient feels. For each dimension, patients select which statement best describes their health on that day from a possible five options of increasing levels of severity (no problems, slight problems, moderate problems, severe problems and unable to/ extreme problems). A visual analogue scale (VAS) which ranges from 0 (worst imaginable health) to 100 (best imaginable health) is used to assess how the patient feels.

The EQ-5D-5L index comprises six questions that cover five dimensions of health (mobility, self-care, usual activities, pain/discomfort and anxiety/depression) and a VAS. A unique health state, the EQ-5D-5L profile, based on the five dimensions is reported as a five-digit code with a possible total of 3,125 health state. For example, state 11111 indicates no problems on any of the five dimensions. This EQ-5D-5L profile will be converted into a weighted health state utility value, termed the EQ-5D index, by applying a country-specific equation to the profile that represents the comparative value of health states. This equation is based on national valuation sets elicited from the general population and the base case will be the UK perspective. Where a valuation set has not been published, the EQ-5D-5L profile will be converted to the EQ-5D index using a crosswalk algorithm (van Hout et al 2012). The visual analogue scale, the EQ-VAS, is reported separately.

The evaluable population will comprise the FAS population.

3.4 Safety

Safety and tolerability will be assessed in terms of AEs (including SAEs), deaths, laboratory data, vital signs, ECG and exposure. These will be collected for all patients.

3.4.1 Adverse events

AEs and SAEswill be collected throughout the study, from informed consent until 30 days after the last dose of olaparib/placebo.

Other significant adverse events (OAE)

During the evaluation of the AE data, an AstraZeneca medically qualified expert will review the list of AEs that were not reported as SAEs and 'Discontinuation of Investigational Product due to Adverse Events' (DAEs). Based on the expert's judgement, significant adverse events of particular clinical importance may, after consultation with the Global Patient Safety Physician, be considered other significant adverse events (OAEs) and reported as such in the CSR. A similar review of laboratory/vital signs/ECG data will be performed for identification of OAEs.

Examples of these are marked haematological and other laboratory abnormalities, and certain events that lead to intervention (other than those already classified as serious), dose reduction or significant additional treatment.

3.4.2 Treatment exposure

Exposure will be defined as follows:

Total (or intended) exposure of olaparib/placebo

• Total (or intended) exposure = last dose date – first dose date + 1

Actual exposure of olaparib/placebo

• Actual exposure = intended exposure – total duration of dose interruptions, where intended exposure will be calculated as above.

3.4.3 Dose intensity

[figure not shown]
Relative dose intensity (RDI) is the percentage of the actual dose intensity delivered relative to the intended dose intensity through to treatment discontinuation. Percentage intended dose (PID) is the percentage of the actual dose delivered relative to the intended dose through to progression. Both will be derived using study treatment data up to three years or until the date of objective disease progression (whichever is earliest) as defined by RECIST using the investigator site assessments. If the investigator considered that it was in the patient's best interest to continue study treatment past this time, this was not included in the derivation of dose intensity.

[figure not shown]
Relative dose intensity (RDI) and percent intended dose (PID) will be defined as follows:

- RDI = 100% * d/D, where d is the actual cumulative dose delivered up to the earlier of progression (or a censoring event) or the actual last day of dosing and D is the intended cumulative dose up to the earlier of progression (or a censoring event) or the actual last day of dosing plus the protocol-defined post-dose rest period.
- PID = 100% * d/D, where d is the actual cumulative dose delivered up to progression (or a censoring event) and D is the intended cumulative dose up to progression (or a censoring event). D is the total dose that would be delivered, if there were no modification to dose or schedule.

Date 15 February 2022

Figure 3 Example of Dose Intensity Calculations for Olaparib

In this example, patients 1-4 progressed or were censored on Day 15. All four patients received less treatment than intended due to:

- Missed/forgotten doses (Patient 1)
- Dose reduction and early stopping (Patient 2)
- Dose interruption (Patient 3)
- Progression whilst on dose interruption (Patient 4)
- Early stopping (Patient 5)

Patient 1: RDI = PID = ((12 * 300 mg * 2) + (2 * 300 mg)) / (14 * 300 mg * 2) = 93%

Patient 2: RDI = ((7 * 300 mg * 2) + (4 * 250 mg * 2)) / (11 * 300 mg * 2) = 94%

Date 15 February 2022

$$PID = ((7 * 300 \text{ mg} * 2) + (4 * 250 \text{ mg} * 2)) / (14 * 300 \text{ mg} * 2) = 74\%$$

Patient 3: RDI = PID =
$$(9 * 300 \text{ mg} * 2) / (14 * 300 \text{ mg} * 2) = 64\%$$

Patient 4: RDI =
$$(12 * 300 \text{ mg} * 2) / (12 * 300 \text{ mg} * 2) = 100\%$$

$$PID = (12 * 300 mg * 2) / (14 * 300 mg * 2) = 86\%$$

Patient 5: RDI =
$$((5 * 300 \text{ mg} * 2) + (1 * 300 \text{ mg})) / (6 * 300 \text{ mg} * 2) = 92\%$$

$$PID = ((5 * 300 \text{ mg} * 2) + (1 * 300 \text{ mg})) / (14 * 300 \text{ mg} * 2) = 39\%$$

